7.6.5 Adverse Events Assessments

7.6.5.1 Performing Adverse Event Assessments

An AE is defined as any untoward medical occurrence in a patient administered a pharmaceutical product (including a study drug) during the course of a clinical investigation. An AE can therefore be any unfavorable and unintended sign (including an abnormal laboratory finding), symptom, or disease temporally associated with the use of a pharmaceutical product, whether or not considered related to the pharmaceutical product.

An elective surgical procedure not associated with a worsening of a known underlying medical condition is not considered an AE, and therefore will not be considered an SAE despite requiring hospitalization. However, complications of the procedure will be considered an AE and may be considered an SAE if hospitalization is prolonged (or any other SAE criteria is met). A hospitalization or prolongation of a hospitalization for reasons other than an AE would not be considered an SAE.

AEs will be found by the patient's spontaneous complaint, patient comment cards, or as a result of non-leading questions, physical examination, vital signs, or laboratory tests. AEs include any occurrences that are new in onset or aggravated in severity or frequency from the baseline condition, or abnormal results of diagnostic procedures, including laboratory test abnormalities. Medical histories which are reported at the baseline and worsen following the exposure to the study drug will be considered as AEs. Lack of efficacy or fluctuation in influenza symptoms will not constitute an AE in this study.

The investigator or subinvestigator is responsible for assessing AEs. AEs should be fully investigated and recorded in detail including start date, end date (if outcome is other than recovering, not recovered, or unknown), severity, seriousness with its category, relationship with the study drug, action taken to manage the AE, and outcome of the AE in the eCRF.

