7.6.5.7 Serious Adverse Events

7.6.5.7.1 Definition

An SAE is defined by regulation as any AE occurring at any dose that results in any of the following outcomes:

Death
Life-threatening condition
Hospitalization or prolongation of existing hospitalization
Persistent or significant disability/incapacity
Congenital anomaly/birth defect
Other medically important condition

Important medical events that may not result in death, be life-threatening, or require hospitalization may be considered as SAE when, based upon appropriate medical judgment, they may jeopardize the patient and may require medical intervention to prevent one of the outcomes listed in this definition. Examples of such medical events include allergic bronchospasm requiring intensive treatment in an emergency room or at home, blood dyscrasias or convulsions that do not result in inpatient hospitalization, or the development of drug dependency or drug abuse. Test results that meet the following criterion are considered as SAE. The investigator or subinvestigator will determine the seriousness of AEs.

AST or ALT > 3 × Upper limit of normal (ULN) and total bilirubin > 2 × ULN.

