7.6.5.7.2 Reporting Serious Adverse Events

All information regarding SAEs, including the SAE itself, associated medications, and SAE narratives, must be entered into electronic data capture (EDC) within 24 hours from the point in time when the investigator first becomes aware of the SAE. If EDC becomes unavailable, all SAEs must be reported to the CRO or sponsor in detail utilizing the SAE

form. Upon availability of EDC, this information must then be entered into EDC. All SAEs must be reported regardless of causal relationship to the study drug. A sample of the SAE form can be found in the Site Regulatory Binder. Follow-up information on the SAE may be requested by the sponsor.

When reporting SAEs, the investigator should record the diagnosis whenever possible. If no diagnosis is available at the time of reporting, individual signs and symptoms can be reported.

In the event of any SAE reported or observed during the study, whether or not attributable to the study drug, site personnel must report within 24 hours. SAEs can be reported by fax, phone, e-mail, or via EDC system (if available).

If follow-up is required or requested, the investigator should enter the new information into EDC. Discharge summaries, consultant reports, autopsy reports, or other relevant documents must be evaluated by the investigator and all relevant information must be included on the follow-up SAE form. Copies of these reports may also be requested by the sponsor.

Appropriate remedial measures should be taken by the investigator using his/her best medical judgment to treat the SAE. These measures and the patient's response to these measures should be recorded. Clinical, laboratory, and diagnostic measures should be employed by the investigator as needed to adequately determine the etiology of the event.

Any SAEs occurring after the AE assessment period specified in Section 7.6.5.2, that are considered to be related to study drug by the investigator must be reported to the CRO or the sponsor.

The investigator will be responsible for reporting all SAEs to the IRB or EC through the head of the study center in accordance with applicable regulatory requirements. The sponsor will be responsible for reporting SAEs to the regulatory authorities as required by the applicable regulatory requirements.

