Defined as the time between the initiation of the study treatment and the resolution of fever. The resolution of fever is defined as the time when the patient’s self-measured axillary temperature becomes less than 37°C and is maintained at less than 37°C for a duration of at least 12 hours.
10. Proportion of patients reporting normal temperature at each time point
Defined as the percentage of patients whose axillary temperature drops to less than 37°C after the initiation of the study treatment in the analysis population.
11. Body temperature at each time point
Defined as measured axillary temperature.

12. Time to alleviation of individual symptoms

Defined as the time between the initiation of the study treatment and the alleviation of individual symptom. The alleviation of a symptom is defined as the time when the symptom is assessed as 0 (None) or 1 (Mild), for duration of at least 21.5 hours (24 hours – 10%).

13. Time to return to preinfluenza health status

Patients will be asked to record their preinfluenza health status between 0 (worst possible health) and 10 (normal health [for someone your age and your health condition]). Then the same information will be taken as part of the eDiary. Return to preinfluenza health status is defined as time from the initiation of the study treatment to time to the same number on scale for preinfluenza health status.

14. Incidence of influenza-related complications

Defined as the percentage of patients in the analysis population who experience each influenza-related complication (hospitalization, death, sinusitis, otitis media, bronchitis, and radiologically confirmed pneumonia) as an AE after the initiation of the study treatment. A specific complication eCRF with diagnostic criteria for the complications of sinusitis, otitis media, bronchitis and pneumonia will be provided.

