Appendix 1 Time and Events Schedule

	Treatment Period										Follow-up Period									
	D1	D2	D3	D4	D5	D6	D7	D8	D9	D10	D11	D12	D13	D14	D15	D22 or ET				
Visit Window (days)	V1	V2	V3	OpV1	V4	OpV2			V5						V6	V7				
Informed Consent/Assent	-	-	+1	-	+1	-			±2						±3	±3				
Inclusion/Exclusion Criteria	X																			
Demographics	X																			
Medical History ^a	X																			
Rapid Influenza Diagnostic Test	X ^b																			
Randomization	X																			
Study Drug Dispensation	X																			
Study Drug Administration	X	X	X	X	X															
Body Temperature Measurement	X ^d	4 Times Daily							Twice Daily											
Assessment of Severity of Influenza Symptoms	X ^d				Twice Daily															
Assessment of Health	X ^d								Once Daily											
Assessment of Health Prior to Influenza Symptoms	X ^d																			
EQ-5D-5L	X ^d				Twice Daily											X				
Work Productivity Questionnaire																				
Assessment of Influenza-related Complications (sinusitis, bronchitis, otitis media, pneumonia)	X	X	X	X	X	X			X						X	X				
Full Physical Examination	X ^{e,f}															X ^e				
Symptom-focused Physical Examination		X	X	X	X	X			X						X					
Concomitant Therapies		X	X	X	X	X			X						X	X				
Study Drug Accountability		X	X	X	X	X														
Urine Pregnancy Test(WOCBP) ^g	X				X											X				
Immunological Tests	X ^h																			
Routine Laboratory Tests	X				X										X	X				
Influenza Antibody Titer Test	X ^h															X				

[figure not shown]
Nasopharyngeal (preferred)/pharyngeal (if nasopharyngeal cannot be collected) Swabs (Virology Test)	X ^h	X	X	X	X	X	X	X	X	X	X	X ⁱ	X ^{i,j}
Vital Sign Measurements	X	X	X	X	X	X	X	X	X	X	X	X	X
Electrocardiography	X	X	X	X	X	X	X	X	X	X	X	X	X
Pharmacokinetic Blood Samples	X ^k	X	X ^k	X	X	X	X	X	X	X	X ^k	X	X
Adverse Event Assessment	X	X	X	X	X	X	X	X	X	X	X	X	X
Interview for Meal Consumption	X	X	X	X	X	X	X	X	X	X	X	X	X
Intrahousehold Infection Interview (for Japan only)	X	X	X	X	X	X	X	X	X	X	X	X	X

D = Day, ET = early termination, V = visit, OpV = optional visit.

- a Prior therapies will also be reviewed.
- b Not necessary if a site has performed a Rapid Influenza Diagnostic Test prior to consideration for the study.

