Body temperature is defined as measured axillary temperature at 12, 24, 36, 48, 72, 96 and 120 hours. Body temperature obtained when e-diary is set up after initial dosing will not be used for analysis. Because these data may be observed due to e-dairy system’s incorrect setting.

17) Time to return to preinfluenza health status (unit: hours)

Patients will be asked to record their preinfluenza health status between 0 (worst possible health) and 10 (normal health [for someone your age and your health condition]). Time to return to preinfluenza health status is defined as the time from the initiation of the study treatment to the first time when health status score is equal to or higher than the preinfluenza health status score. Patients who have

smaller number on scale for preinfluenza health status by the last observation time point will be censored at that time point. If preinfluenza health status is missing at date and time of assessment that patients have, missing assessments of preinfluenza health status conservatively will be treated as having less than preinfluenza health status at the corresponding date and time of assessment.

Patients whose health status score at baseline is equal to or higher than the preinfluenza health status score will be excluded from the analysis. Health status score obtained when e-diary is set up after initial dosing will not be used for analysis. Because these data may be observed due to e-dairy system's incorrect setting.

18) Incidence of influenza-related complications (unit: %)

This endpoint is defined as the percentage of patients who experience each influenza-related complication (hospitalization, death, sinusitis, otitis media, bronchitis, and radiologically confirmed pneumonia) as an AE after the initiation of the study treatment. A specific complication eCRF with diagnostic criteria for the complications of sinusitis, otitis media, bronchitis and pneumonia will be provided as following rules.

- Sinusitis
  - 'Sinusitis' in the 'Form Incidence of influenza-related complications' is 'Yes'
  - And 'Did these symptoms start after the influenza treatment was given on Day 1?' in the 'Form Sinusitis' is 'Yes'
  - And 'Does the patient have a purulent nasal discharge?' in the 'Form Sinusitis' is 'Yes'
  - And 'Does the patient have facial pain, pressure sensation, or sensation of fullness?' in the 'Form Sinusitis' is 'Yes'

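### A hospital admission for worsening influenza can be classed as an AE or as lack of efficacy; under the second reading it leaves both the SAE reports and the hospitalisation component of the complications endpoint.

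*Protocol*

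**What the plan says.** Protocol 7.6.5.1 contains an inclusion and an exclusion in one paragraph. The inclusion is "AEs include any occurrences that are new in onset or aggravated in severity or frequency from the baseline condition". The exclusion, which closes the paragraph, is "Lack of efficacy or fluctuation in influenza symptoms will not constitute an AE in this study". It carries no qualification for events that end in admission or death.

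The preceding paragraph of that section says "A hospitalization or prolongation of a hospitalization for reasons other than an AE would not be considered an SAE". Section 7.6.5.7.1 is built the same way: "An SAE is defined by regulation as any AE occurring at any dose that results in any of the following outcomes". Section 7.6.5.7.2 adds "All SAEs must be reported regardless of causal relationship to the study drug", but that duty starts only once the event is an AE.

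The complications endpoint (Protocol 9.10.2 item 14, repeated in SAP 9.2 item 18) is the percentage of patients "who experience each influenza-related complication (hospitalization, death, sinusitis, otitis media, bronchitis, and radiologically confirmed pneumonia) as an AE". Each component is compared by Fisher's exact test. SAP 10.1 defines death as an AE with a fatal outcome.

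The complications eCRF is described as holding diagnostic criteria for sinusitis, otitis media, bronchitis and pneumonia. The visit check in Protocol 7.6.1 and the matching row of Appendix 1 name the same four. SAP 9.2 item 18 gives derivation rules for those four and none for hospitalisation or death.

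**The concern.** Protocol 7.8.1 expects that some patients will deteriorate or not respond, and lists progression of influenza among the explanations to consider. It does not say whether such a case is an AE. A site that reads the exclusion in 7.6.5.1 literally could decide that an admission for influenza itself is lack of efficacy. Another site, with an identical patient, could decide that it is an aggravation from baseline.

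Two things depend on that choice. One is whether the admission reaches the sponsor as an SAE within 24 hours; the trial has no data monitoring committee (10.9.1) and no interim analysis (9.14). The other is whether the admission counts in a tested component of a secondary endpoint. Admissions for influenza are an obvious part of what a hospitalisation component is for, yet they are the ones that the exclusion can reach.

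**Working it through.** The main check is a comparison of texts. Take a patient admitted after the first dose because the influenza has worsened, with none of the four named diagnoses, and follow both readings.

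| Step | Classed as aggravated from baseline | Classed as lack of efficacy or fluctuation |
|---|---|---|
| AE (Protocol 7.6.5.1) | Yes | No |
| SAE (7.6.5.1, 7.6.5.7.1) | Yes, through hospitalisation | No, since an SAE must first be an AE |
| 24-hour SAE report (7.6.5.7.2) | Required | Not required |
| Hospitalisation component (Protocol 9.10.2 item 14; SAP 9.2 item 18) | Counted | Not counted, because of the AE condition |
| AE and SAE tables (SAP 10.1) | Counted | Not counted |

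**Is there another source?** The described eCRF criteria, the visit check and the SAP derivation rules cover four diagnoses, and this patient has none of them. Reasons for withdrawal are collected (7.8) and appear in the disposition table, but they do not feed the endpoint. The SAP also keeps the two categories apart: the sensitivity analyses in 6.4 and 9.1.1.4 list AE and lack of efficacy as separate reasons for discontinuation. No described source for the hospitalisation component bypasses the AE record.

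**Death.** No sentence excludes a death. To lose one, an investigator would have to regard a fatal course as lack of efficacy or symptom fluctuation, which is a strained reading. It remains true that the endpoint and the SAP 10.1 death count both require an AE record.

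**Size.** The plan states no expected rate of hospitalisation, so there is no figure to reproduce. The endpoint is analysed in the ITTI population (Protocol 9.10.3, SAP 9.4). The planned numbers come from Protocol 9.2:

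- Placebo: 31 + 175 = 206
- S-033188: 62 + 350 = 412

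Assume that between 0.2% and 1% of patients are admitted for influenza. This range is an assumption; nothing in the documents supports a particular value.

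- Placebo: 206 × 0.002 = 0.4; 206 × 0.01 = 2.1
- S-033188: 412 × 0.002 = 0.8; 412 × 0.01 = 4.1

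With expected counts of this size, misclassifying a few admissions could leave the hospitalisation row empty.

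**The case against.** The strongest reply is that the protocol already treats influenza-related hospitalisation and death as AEs. The endpoint names both as complications, so the AE condition may be an instruction to record them as AEs rather than a filter. The exclusion mentions lack of efficacy and fluctuation, not progression, admission or death. Because symptoms are rated in the diary, the sentence is reasonably read as keeping diary ratings out of the AE tables. The sentence on admissions for other reasons closes a paragraph on elective surgery and adds nothing once AE status is settled. This stands in part: a careful investigator may well report the admission, so loss is possible, not required. It does not remove the problem, because the exclusion is the more specific sentence, has no seriousness exception, and is never reconciled with the inclusion beside it.

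Three stronger inferences are tempting, and the documents do not support them.

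- *That deaths are lost as readily as admissions.* They are less exposed, as shown above.
- *That the sponsor would not hear of these cases quickly.* Section 7.8.1 asks for urgent discussion with the sponsor or Medical Monitors when the investigator wishes to give open-label oseltamivir for non-response, and 7.8 requires prompt notice of withdrawals. These routes cover some of the cases but not all, and they are not SAE reports.
- *That the comparison is biased towards no difference.* That would need more such admissions on placebo and a known pattern of loss. The documents give neither.

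It is also fair to say that the full content of the complications form is not shown, so it may already hold fields for hospitalisation and death. Finally, the significance test would seldom turn on this. If there were only two admissions and both were on placebo, Fisher's two-sided p would be (206 × 205)/(618 × 617) = 0.11. What is at risk is the reported count and the SAE record.

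**Conclusion.** The point holds as an unresolved conflict in the recording rules. Protocol 7.6.5.1 lets an admission for worsening influenza be classed as an AE or as lack of efficacy. Under the second reading it is neither an SAE nor an event in the hospitalisation component. For hospitalisation the path follows directly from the text; for death it is only inferred.

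The number affected cannot be estimated from the documents. Under the assumed 0.2% to 1%, about 0.4 to 2.1 placebo and 0.8 to 4.1 S-033188 patients in the planned ITTI population would be admitted, and only those classed as lack of efficacy would be lost. The range could be too high, since the trial excludes severe influenza needing inpatient treatment and patients with listed risk factors. The direction of any bias is not established. The change is worth making because the text, applied literally, can drop serious events and the remedy is cheap.

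**What to change.** 1. **Protocol 7.6.5.1.** Extend the excluding sentence so that lack of efficacy or fluctuation in influenza symptoms is not an AE *unless the event meets an SAE criterion, in which case it is recorded and reported as an SAE*.
2. **Protocol 9.10.2 item 14 and SAP 9.2 item 18.** Count hospitalisation and death after the first dose whether or not coded as an AE, and record the reason. The reason lets admissions unrelated to influenza, such as elective surgery, be shown separately.
3. **Complications eCRF.** If they are not already there, add hospitalisation and death (yes/no, date, reason).

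The cost is one clause in 7.6.5.1, matching edits to the endpoint definition in both documents, and a few eCRF fields. The downside is a few more SAE reports for disease progression. The changes affect recording and counting only, not patient care.

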7.6.5.2 Timing

AEs will be collected from the time of informed consent through Visit 7 (Day 22). If a patient withdraws early from the study, the investigator or subinvestigator will make an effort to collect AEs for 21 days after the last dose of the study drug. All AEs will be followed until resolution, stabilization, the condition becomes chronic, or 35 days after the last study drug administration. Serious treatment-related AEs or AEs related to abnormal liver function tests shown in Appendix 5 will be followed until resolution, stabilization, the condition becomes chronic, or the patient becomes lost to follow-up.

7.6.5.3 Severity

The severity of an event will be categorized by the investigator or subinvestigator according to the following definitions based on the Common Terminology Criteria for Adverse Events (CTCAE) Version 4.0 [11]:

Grade 1:	Mild; asymptomatic or mild symptoms; clinical or diagnostic observations only; intervention not indicated
Grade 2:	Moderate; minimal, local, or noninvasive intervention indicated; limiting age-appropriate instrumental Activities of Daily Living (ADL)*
Grade 3:	Severe or medically significant but not immediately life-threatening; hospitalization or prolongation of hospitalization indicated; disabling; limiting self-care ADL**
Grade 4:	Life-threatening consequences; urgent intervention indicated
Grade 5:	Death related to AE

* Instrumental ADLs refer to preparing meals, shopping for groceries or clothes, using the telephone, managing money, etc.

** Self-care ADLs refer to bathing, dressing and undressing, feeding self, using the toilet, taking medications, and not bedridden.

The highest severity during the period in which the AE occurred will be recorded in the eCRF.

7.6.5.4 Relationship

The relationship of an event to the study drug will be determined by the investigator or subinvestigator according to the following criteria:

Related:	An AE which can be reasonably explained as having been caused by the study drug. For example, a similar event has been reported previously, or increase/decrease of the dose affects the occurrence or seriousness of the AE, etc.
Not related:	An AE which cannot be reasonably explained as having been caused by the study drug.

7.6.5.5 Expectedness

A treatment-related AE is considered expected if it is listed in the subsection “Expected Adverse Reactions” under the section “Undesirable Effects” of “SUMMARY OF DATA AND GUIDANCE FOR INVESTIGATORS” in the current investigator's brochure (IB) for S-033188. The current version of the Prescribing Information for Tamiflu[®] (oseltamivir phosphate) capsules/Tamiflu[®] for oral suspension should also be used for oseltamivir expectedness assessments. Expectedness will be assessed by the sponsor.

7.6.5.6 Adverse Event Assessment of Clinical Laboratory and Other Safety Parameters

For any abnormal laboratory test results (hematology, blood chemistry, or urinalysis) or other safety assessments (eg, physical examination, vital signs, ECG) that vary following exposure to the study drug from baseline, the investigator or subinvestigator will determine whether these results are clinically significant. Abnormal laboratory test results are defined as value outside the reference range. For test results which are abnormal at baseline and worsen following the initiation of the study, the investigator or subinvestigator must also determine whether these results are clinically significant. Any test results which are considered to be clinically significant by the investigator or

subinvestigator will be recorded as AEs. If the abnormal laboratory finding is associated with a disease or organ toxicity, the investigator should report only the disease or organ toxicity as AEs.

The investigator or subinvestigator will consider test results to be clinically significant in the following circumstances:

- Test result leads to any of the outcomes included in the definition of an SAE (see Section 7.6.5.7).
- Test result leads to a concomitant drug treatment or other therapy.
- Test result requires additional diagnostic testing or other medical intervention.
- Test result meets the management and discontinuation criteria for abnormal liver function tests (Appendix 5).

Test results meeting the management and discontinuation criteria for abnormal liver function tests (Appendix 5) will require evaluation and additional testing, and the results will be recorded on the liver function abnormality follow-up form.

